7.11.5. Vital Signs

Vital signs and changes from baseline values will be summarized by visit and within treatment arm using mean, standard deviation, median, minimum and maximum values. Results will be summarized at baseline, on Day 1 of each dosing cycle, and every 7 days thereafter. A patient's most recent test result will be carried forward and included in analyses on days when vital signs were not assessed. Typical comparisons of results summarized by visit may have limited interpretability for the same reasons outlined in section 7.11.4. Therefore, vital signs will be analyzed separately for the four groups identified there.

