7.2. Missing Values

In general, missing values will not be replaced by imputed values.

- Although the central hematologists' assessment of response is the primary evaluation, the local assessment (i.e., the one recorded at the study center where the patient is enrolled) will be used for patients who are missing an evaluation from the central hematologists (see section 7.9.1)
- Patients who, for any reason, do not supply bone marrow for response assessment are counted among those not achieving remission
- Patients missing a time-to-event endpoint will have their value censored according to the rules set forth below (see sections 7.9.2 to 7.9.6)

Exceptions to the general rule of not replacing missing values are planned for the following items.

- The first day of the month will be used for a missing day component of a partial birthdate, and January will be substituted for a missing birth month (these substitutions are relevant only for calculating a patient's age)
- Partial start and end dates for adverse events will be replaced by calendar dates that maximize the duration of the adverse event (see section 7.11.2)
- Missing clinical laboratory parameters and vital signs will be replaced using the "last value carried forward" method (see sections 7.11.4 and 7.11.5, respectively)

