7.11.4. Clinical Laboratory Parameters

Typical comparisons of results summarized by visit may have limited interpretability in this study because (1) study drugs from the two treatment arms are administered on

different cycle days (Days 1-9 for ACM versus Days 1-4 for CM), (2) the schedule for clinical laboratory evaluations (cycle day and frequency) is different between the treatment arms, and (3) additional cycles of treatment start according to patients' response to treatment rather than based on a predetermined schedule. Therefore, four groups of laboratory data will be summarized separately:

- Cycle 1 results (from all patients in the safety population) up to the day a patient starts Cycle 2 or 10 weeks after starting Cycle 1, whichever comes first
- Cycle 2 results (from patients in the safety population who receive at least 2 cycles of study drug) up to the day a patient starts Cycle 3 or 10 weeks after starting Cycle 2, whichever comes first
- Cycle 3 results (from patients in the safety population who receive at least 3 cycles of study drug) up to the day a patient starts Cycle 4 or 10 weeks after starting Cycle 3, whichever comes first
- Cycle 4 results (from patients in the safety population who receive 4 cycles of study drug) up to 10 weeks after starting Cycle 4

Laboratory test results measured on a continuous scale and changes from baseline values will be summarized within treatment arm using mean, standard deviation, median, minimum and maximum values. Results will be summarized at baseline, on Days 1-9, and every 7 days starting with Day 15 for patients receiving ACM, and at baseline, on Days 1-4, and every 7 days starting with Day 8 for patients receiving CM. Up to the point of starting a new treatment cycle or withdrawing from the study, a patient's most recent test result will be carried forward and included in analyses on days when clinical laboratory testing was not performed.

Ordinal categorical test results will be summarized within treatment arm using shift tables. Additionally, for tests where CTCAE [version 4.03] severity criteria are specified, CTCAE severity grades will be summarized in shift tables.

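### The vital-signs carry-forward rule in SAP 7.11.5 has no stop at death or withdrawal, and it fills the ACM Day 8 summary with the baseline reading

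*SAP*

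**What the plan says.** SAP 7.2 sets a general rule against imputation and then lists exceptions. One of them reads "Missing clinical laboratory parameters and vital signs will be replaced using the" last-value-carried-forward method, and it points to 7.11.4 for laboratory data and 7.11.5 for vital signs.

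For laboratory data, 7.11.4 fills untested days with the latest available value, but its rule opens with a limit: "Up to the point of starting a new treatment cycle or withdrawing from the study". The section also divides the data into four cycle groups. The first runs "up to the day a patient starts Cycle 2 or 10 weeks after starting Cycle 1, whichever comes first", and the others follow the same pattern.

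For vital signs, 7.11.5 has almost the same sentence without the opening clause: a patient's "most recent test result will be carried forward and included in analyses on days when vital signs were not assessed". The time grid is: "Results will be summarized at baseline, on Day 1 of each dosing cycle, and every 7 days thereafter". The section then borrows the laboratory grouping: "Therefore, vital signs will be analyzed separately for the four groups identified there".

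SAP 7.3 says visit windows will be used for both data types and refers to these two sections, but 7.11.5 gives no window widths. Protocol 11.4.4 plans by-visit summaries of vital signs and does not mention carry-forward.

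**The concern.** Two things go wrong if 7.11.5 is programmed as written.

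First, nothing ends the series when a patient dies or leaves. The last reading keeps entering the weekly means and standard deviations until the cycle group closes. The number of values behind each summary then exceeds the number of patients still being measured. SAP section 7 plans 95% confidence intervals for means, and the continuous-data template in Appendix 2 drops only the p-value for safety tables, so those intervals would look tighter than the data allow.

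Second, the weekly grid does not match the visit schedule early in Cycle 1. Where a grid day has no scheduled reading, the rule supplies the previous one. At ACM Day 8 that is the pre-dose baseline, so the table would report no change from baseline during treatment because of the rule and not because of any measurement.

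**Working it through.** The plan gives no figure to reproduce, so the check compares the texts and counts grid points.

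**1. Stopping rules compared**

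| | Laboratory (7.11.4) | Vital signs (7.11.5) |
|---|---|---|
| Fills unassessed days | Yes | Yes |
| Stops at a new cycle | Stated | Through the cycle groups |
| Stops at withdrawal | Stated | Not stated |
| Stops at death | By implication: protocol 6.2 lists death among reasons for removal | Not stated |
| Outer limit | Next cycle or 10 weeks | The same, by reference |

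**2. Points filled after an exit in Cycle 1**

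Inputs: the weekly grid of 7.11.5 and the 10-week limit of 7.11.4. Taking 10 weeks after Day 1 as Day 71, the grid days are 1 + 7k for k = 0 to 10: Days 1, 8, 15, 22, 29, 36, 43, 50, 57, 64 and 71. Ten of these fall after Day 1.

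For a patient who exits on day d without starting Cycle 2, the number of later grid points is 10 − floor((d − 1)/7):

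- Day 20: 10 − floor(19/7) = 10 − 2 = 8 of 10
- Day 30: 10 − floor(29/7) = 10 − 4 = 6 of 10 (Days 36, 43, 50, 57, 64, 71)
- Day 45: 10 − floor(44/7) = 10 − 6 = 4 of 10
- Day 60: 10 − floor(59/7) = 10 − 8 = 2 of 10

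The exit days are illustrations. Day 45 is the latest nominal day for the Cycle 1 marrow, so the Day 45 row shows what can happen when a patient is removed for non-response. The problem does not depend on deaths alone.

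**3. Grid against schedule, Stage 2 Cycle 1**

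- Protocol 5.4.1.2 schedules vital signs just before the first dose.
- Protocol 5.4.2.1, the daily in-hospital list, does not include them.
- Protocol 5.4.3 schedules them weekly once chemotherapy is complete. Appendix A agrees on all three.
- ACM runs over Days 1-9, so no weekly post-chemotherapy visit can fall on or before Day 8. The value at ACM Day 8 is the Day 1 pre-dose reading.
- The SAP defines baseline as the last value before the first dose, which is that same reading. Change at ACM Day 8 = baseline − baseline = 0.

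Other days depend on when the first weekly visit falls. If it comes 7 days after the last chemotherapy day (assumed: ACM Day 9 + 7 = Day 16; CM Day 4 + 7 = Day 11), the grid days with no earlier post-dose reading are Days 8 and 15 for ACM and Day 8 for CM. Defined windows could move these readings onto the grid. Only ACM Day 8 follows from the schedule without this assumption.

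**4. Patients who might be affected by death (assumption only)**

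Protocol 2.8 cites treatment-related mortality of about 8-10% in earlier studies, and up to 28% in Study 6. Protocol 11.2.2 plans 28 patients per arm.

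- 0.08 × 28 = 2.24
- 0.10 × 28 = 2.8
- 0.28 × 28 = 7.84

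This gives about 2 to 8 ACM patients if those rates carried over. It counts possible deaths and does not measure bias in any mean.

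**The case against.** The strongest reply is that this is one dropped clause. SAP 7.2 presents a single method for both data types, and 7.11.5 adopts the reasoning and grouping of 7.11.4, so the authors probably meant the same stop to apply. That is a fair view of intent. It does not change what 7.11.5 tells a programmer to do, and it supports adding the clause.

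The SAP also admits that by-visit comparisons may be hard to interpret, because dosing days and schedules differ by arm, and it promises visit windows in 7.3. Both points stand. The caveat does not remove readings taken before a patient left, however, and the windows have no widths in 7.11.5.

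A reader might infer four stronger things that the documents do not support:

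- **That readings are carried without limit.** They are not; the series ends at the next cycle or at 10 weeks.
- **That the laboratory rule has the same fault.** It stops at withdrawal, which covers death by implication, and it uses arm-specific days that broadly follow the daily-then-weekly schedule for hematology and tumor lysis labs. Some untested laboratory days are still filled, but that is a lesser concern.
- **That 2 to 8 patients will contribute readings after death.** The rates are treatment-related, not all-cause, and come from other populations. Protocol 2.8 links the high figure particularly to patients over 60, and Study 6 enrolled to age 70, whereas this trial stops at 65. There is no matching figure for CM. The SAP still plans 53 per arm, so even the denominator is unsettled.
- **That the trial's safety conclusions are compromised.** Adverse event incidence, tumor lysis classification and 30- and 60-day mortality do not use these by-visit means. Shift tables take the most extreme post-baseline result, and repeating an existing reading cannot make it more extreme.

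**Conclusion.** The point holds for vital signs. As written, 7.11.5 lets patients who have died or withdrawn keep contributing readings up to the next-cycle or 10-week limit, for example at 6 of 10 post-Day-1 weekly points after an exit on Day 30. In Stage 2 Cycle 1 it also makes the ACM Day 8 summary a copy of baseline, unless unscheduled readings were recorded.

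This is a minor fault. It is confined to descriptive by-visit vital-sign tables; no hypothesis test, significance level or power figure depends on it. The grid counts rest on taking Day 71 as the 10-week limit and on the illustrative exit days. The number of patients affected, and the shift in any mean, cannot be established from the documents.

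**What to change.** In SAP 7.11.5, summarise observed vital signs only, state the widths of the windows promised in 7.3, and show n at each time point. Amend the 7.2 exception so that it no longer covers vital signs.

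If carry-forward is kept, repeat in 7.11.5 the stop at a new cycle or withdrawal from 7.11.4 and name death explicitly. This alternative does not cure the ACM Day 8 problem, so that table should also show how many values were observed.

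The cost is a smaller n at some visits, and possibly none at ACM Day 8, which would reflect what was measured. Programming becomes simpler. The SAP was written against Amendment 7 and the protocol has since reached Amendment 11, so the change can go into a revision that is needed anyway.

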7.11.6. Concomitant Medication Use

Optionally, depending on the perceived relevance, concomitant medications will be mapped to terminology in the WHO DDE and then summarized within treatment arm by usage rates for each level-1 ATC term and preferred (i.e., standardized) drug name.

7.12. Subgroup Analyses

8. Adverse Event and Medication Coding Dictionaries

The MedDRA and WHO DD versions (editions) that will be used to standardize medical terminology are not known at this time, but both will be recent editions published within 2 years before the date the first patient is randomized into the study and the versions used will be documented in the clinical study report.

9. Summary Tables

Suggested titles for summary tables to be included in the clinical study report are shown in Table 9 and blueprints for the format and content of these tables are presented in Appendix 2.

Table 9. Planned Summary Tables

Summary Table [comments]	Patient Population		
	ITT	Safety	Per-Protocol
Patient Disposition	X		
Demography	X	X	X
AML History	X	X	X
Medical History	X	X	X
Pre-Existing Medical Conditions	X	X	X
Relevant Prestudy Medications	X	X	X
Study Drug Exposure	X	X	X
Complete Remission Rates – Independent Hematologists Review [repeat as needed for subgroup analyses]	X		X
Complete Remission Rates – Local Investigator Review [repeat as needed for subgroup analyses]	X		X
Combined CR and Combined Remission Rates – Independent Hematologists Review [repeat as needed for subgroup analyses]	X		X
Combined CR and Combined Remission Rates – Local Investigator Review [repeat as needed for subgroup analyses]	X		X
Correlation Between Independent Hematologists and Local Investigator Reviews – Complete Remission	X		X
Correlation Between Independent Hematologists and Local Investigator Reviews – All Levels of Remission	X		X
Progression-Free Survival [repeat as needed for subgroup analyses]	X		X
Progression-Free Survival Censoring at Transplant [repeat as needed for subgroup analyses]	X		X
Overall Survival [repeat as needed for subgroup analyses]	X		X
Overall Survival Censoring at Transplant [repeat as needed for subgroup analyses]	X		X

Summary Table [comments]	Patient Population		
	ITT	Safety	Per-Protocol
Relapse-Free Survival Following CR [repeat as needed for subgroup analyses]	X		X
Relapse-Free Survival Following CR Censoring at Transplant [repeat as needed for subgroup analyses]	X		X
Relapse-Free Survival Following Combined CR [repeat as needed for subgroup analyses]	X		X
Relapse-Free Survival Following Combined CR Censoring at Transplant [repeat as needed for subgroup analyses]	X		X
Relapse-Free Survival Following Combined Remission [repeat as needed for subgroup analyses]	X		X
Relapse-Free Survival Following Combined Remission Censoring at Transplant [repeat as needed for subgroup analyses]	X		X
Complete Remission Duration [repeat as needed for subgroup analyses]	X		X
Complete Remission Duration Censoring at Transplant [repeat as needed for subgroup analyses]	X		X
Combined Complete Remission Duration [repeat as needed for subgroup analyses]	X		X
Combined Complete Remission Duration Censoring at Transplant [repeat as needed for subgroup analyses]	X		X
Combined Remission Duration [repeat as needed for subgroup analyses]	X		X
Combined Remission Duration Censoring at Transplant [repeat as needed for subgroup analyses]	X		X
Stem Cell Transplant Rates	X		X
ECOG Performance Status Shift Table	X		X
30- and 60-Day Mortality		X	
Numbers of Patients with Adverse Events		X	
Treatment-Emergent Adverse Events: Incidence Rates by MedDRA System Organ Class		X	
Treatment-Emergent Adverse Events: Incidence Rates by MedDRA Preferred Term		X	
Treatment-Emergent Adverse Events Judged Related to Study Drug: Incidence Rates by MedDRA System Organ Class		X	
Treatment-Emergent Adverse Events Judged Related to Study Drug: Incidence Rates by MedDRA Preferred Term		X	

Summary Table [comments]	Patient Population		
	ITT	Safety	Per-Protocol
Treatment-Emergent Adverse Events in the Standardized MedDRA Query for Tumor Lysis Syndrome: Incidence Rates by MedDRA Preferred Term		X	
Treatment-Emergent Adverse Events in the Standardized MedDRA Query for Tumor Lysis Syndrome Judged Related to Study Drug: Incidence Rates by MedDRA Preferred Term		X	
Serious Adverse Events: Incidence Rates by MedDRA System Organ Class		X	
Serious Adverse Events: Incidence Rates by MedDRA Preferred Term		X	
Serious Adverse Events Judged Related to Study Drug: Incidence Rates by MedDRA System Organ Class		X	
Serious Adverse Events Judged Related to Study Drug: Incidence Rates by MedDRA Preferred Term		X	
Treatment-Emergent Adverse Events Leading to a Delay in the Administration of Study Drug: Incidence Rates by MedDRA Preferred Term		X	
Treatment-Emergent Adverse Events Leading to a Reduction in the Protocol-Specified Dose of Study Drug: Incidence Rates by MedDRA Preferred Term		X	
Treatment-Emergent Adverse Events Leading to Discontinuation of Study Drug: Incidence Rates by MedDRA Preferred Term		X	

Appendix 1. Criteria for Grading Severity of Clinical Tumor Lysis Syndrome

	Grade 1	Grade 2	Grade 3	Grade 4	Grade 5
Renal	Creatinine $\leq 1.5 \times \text{ULN}$	Creatinine $> 1.5\text{-}3.0 \times \text{ULN}$	Creatinine $> 3.0\text{-}6.0 \times \text{ULN}$	Creatinine $> 6.0 \times \text{ULN}$	Death
Cardiac Arrhythmia	Intervention not indicated	Non-urgent medical intervention indicated	Symptomatic and incompletely controlled medically or controlled with device (e.g., defibrillator)	Life-threatening (e.g., arrhythmia associated with CHF, hypotension, syncope, shock)	Death
Seizure	—	One brief generalized seizure; seizure(s) well controlled by anticonvulsants or infrequent focal motor seizures not interfering with activities of daily living	Seizure in which consciousness is altered; poorly controlled seizure disorder; with breakthrough generalized seizures despite medical intervention	Seizures of any kind which are prolonged, repetitive or difficult to control (e.g., status epilepticus, intractable epilepsy)	Death

Clinical TLS requires one or more clinical manifestations (renal, cardiac, neuro) along with criteria for laboratory TLS

Maximal clinical manifestation defines the severity grade

ULN = upper limit of normal; 14.4 and 105.6 $\mu\text{mol/L}$ will be used for males and females, respectively, if ULN is not available for an institution

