4.4.2 Inclusion Criteria

To be eligible for participation in the study, patients must meet all of the following inclusion criteria:

During Prescreening:

1. Be between the ages of ≥ 18 and ≤ 65 years
2. Have an established, pathologically confirmed diagnoses of AML by World Health Organization (WHO) criteria excluding acute promyelocytic leukemia (APL-M3) with a bone marrow of $>5\%$ blasts based on histology or flow cytometry
3. Be in first relapse (within 24 months of CR) or have failed induction therapy* (no CR or CRi after treatment with an intensive regimen [eg, anthracycline/cytarabine \pm etoposide, gemtuzumab ozogamicin, or cladribine])
*Induction therapy may involve 1 or 2 cycles of the same regimen. Efficacy assessment of induction therapy must be >21 days from the start of the previous induction cycle.
4. Demonstrate MCL-1 dependence of $\geq 30\%$ by mitochondrial profiling in bone marrow

During Screening:

5. Have an Eastern Cooperative Oncology Group (ECOG) performance status (PS) ≤ 2
6. Have a serum creatinine level ≤ 1.8 mg/dL
7. Have an alanine aminotransferase (ALT)/aspartate aminotransferase (AST) level ≤ 5 times upper limit of normal (ULN)
8. Have a total bilirubin level ≤ 2.0 mg/dL (unless secondary to Gilbert syndrome, hemolysis, or leukemia)
9. Have a left ventricular ejection fraction (LVEF) $>45\%$ by echocardiogram (ECHO) or multigated acquisition (MUGA) scan
10. Be nonfertile or agree to use an adequate method of contraception. Sexually active patients and their partners must use an effective method of contraception associated with a low failure rate during and for at least 6 months after completion of study therapy (see *Section 4.7.3*).

11. Be able to comply with the requirements of the entire study.
12. Provide written informed consent prior to any study related procedure. (In the event that the patient is re-screened for study participation or a protocol amendment alters the care of an ongoing patient, a new informed consent form must be signed.)

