7.11.3. Classification of Tumor Lysis Syndrome

Cairo-Bishop definitions for laboratory TLS and clinical TLS will be used to diagnose and grade TLS.¹⁴ Patients are classified as experiencing laboratory TLS if they have any two or more serum values of uric acid, potassium, phosphorus and/or calcium shown in Table 8 within 3 days before or 7 days after the initiation of study drug.

Table 8. Cairo-Bishop Definition of Laboratory Tumor Lysis Syndrome

Laboratory Parameter	Criteria
Uric Acid	≥476 μmol/L or 25% increase from baseline
Potassium	≥6.0 mmol/L or 25% increase from baseline
Phosphorus	≥1.45 mmol/L or 25% increase from baseline
Calcium	≤1.75 mmol/L or 25% decrease from baseline

Diagnosis of clinical TLS requires the presence of laboratory TLS and elevated serum creatinine levels, cardiac arrhythmia and/or seizures. Criteria for grading the severity of clinical TLS are presented in Appendix 1.

The numbers of patients experiencing laboratory TLS and the various severities of clinical TLS will be summarized within and between treatment arms.

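### As printed, the SAP's fallback creatinine ULN for men (14.4 µmol/L) would give false Grade 3–4 clinical TLS in men with laboratory TLS whose institution's ULN is missing

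*SAP*

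**What the plan says.** SAP 7.11.3 defines TLS in two steps. Laboratory TLS needs at least two of four serum abnormalities (uric acid, potassium, phosphorus, calcium) in a window around the start of study drug. For the second step, "Diagnosis of clinical TLS requires the presence of laboratory TLS and elevated serum creatinine levels, cardiac arrhythmia and/or seizures". Severity is then graded from Appendix 1, which repeats the condition: "Clinical TLS requires one or more clinical manifestations (renal, cardiac, neuro) along with criteria for laboratory TLS".

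In the renal row of Appendix 1, Grade 1 is up to 1.5 × ULN, Grade 2 runs from there to 3.0 ×, Grade 3 to 6.0 ×, and Grade 4 lies above 6.0 ×. Across the renal, cardiac and seizure rows, "Maximal clinical manifestation defines the severity grade".

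The footnote to the table reads "ULN = upper limit of normal; 14.4 and 105.6" µmol/L, and says that these values "will be used for males and females, respectively, if ULN is not available for an institution". No other section of either document gives a different male limit.

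SAP Table 1 lists presence and severity of TLS as a safety endpoint. SAP Table 9 plans two TLS tables by maximum grade (Cycle 1 and whole study), and Appendix 2 gives their layout by arm.

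**The concern.** The two fallback limits refer to the same analyte in the same unit, yet the male one is about one seventh of the female one. Every renal grade is a multiple of this limit, so a denominator that is far too small moves ordinary creatinine values into the top two grades. Because the worst of the three manifestations sets the overall grade, the false renal grade becomes a floor for the patient's TLS grade.

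A man who belongs in the laboratory-TLS-only row, or in a low clinical grade, could therefore be tabulated as Grade 3 or 4. What is at stake is the accuracy of the severity tables for a named safety endpoint.

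**Working it through.** **Inputs**
- Fallback ULN: 14.4 µmol/L (men) and 105.6 µmol/L (women), SAP Appendix 1 footnote.
- Renal cut-points: 1.5, 3.0 and 6.0 × ULN, SAP Appendix 1.
- Entry limit, Protocol 4.4.2: "Have a serum creatinine level ≤ 1.8 mg/dL".
- Unit conversion: 88 to 88.4 µmol/L per mg/dL. This is an assumption; the documents give none.

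The ULN is a stated constant, so the plan has no calculation to reproduce. The check is the ratio creatinine / ULN against the cut-points.

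**Step 1. The two defaults compared**
- 105.6 / 14.4 = 7.33.
- At 88 µmol/L per mg/dL, 105.6 / 88 = 1.20 mg/dL and 14.4 / 88 = 0.16 mg/dL.

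**Step 2. Where the male grades start with ULN = 14.4**
- Grade 2: above 1.5 × 14.4 = 21.6 µmol/L (about 0.24 mg/dL).
- Grade 3: above 3.0 × 14.4 = 43.2 µmol/L (about 0.49 mg/dL).
- Grade 4: above 6.0 × 14.4 = 86.4 µmol/L (about 0.98 mg/dL).

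**Step 3. The same creatinine in a man and a woman, both on the fallback**

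| Creatinine | Man: multiple of 14.4 | Renal band | Woman: multiple of 105.6 | Renal band |
|---|---|---|---|---|
| 0.8 mg/dL (illustrative) | 4.89–4.91 | Grade 3 | 0.67 | not above ULN |
| 1.0 mg/dL (illustrative) | 6.11–6.14 | Grade 4 | 0.83–0.84 | not above ULN |
| 105.6 µmol/L (SAP female ULN) | 7.33 | Grade 4 | 1.00 | not above ULN |
| 1.8 mg/dL (entry limit) | 11.0–11.05 | Grade 4 | 1.50–1.51 | on the Grade 1/2 cut-point |

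Ranges reflect the two conversion factors. The 0.8 and 1.0 mg/dL rows are my illustrations; the last two rows use the documents' own anchors.

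**Step 4. Does the elevated-creatinine condition in 7.11.3 protect these men?** The SAP does not say what creatinine must be elevated against.
- If it means above the ULN in use, any male creatinine above 14.4 µmol/L passes, so the condition screens out almost nobody.
- If it is judged by some other yardstick, men with normal creatinine are not brought in through the renal route. But a man whose creatinine is judged elevated because it exceeds, say, 105.6 µmol/L is already beyond 7.33 × ULN and is graded 4, however small the rise.

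The misgrading survives either reading.

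**Step 5. What a plausible male limit would do**
- Over an assumed male ULN of 90–144 µmol/L, a creatinine of 105.6 is 0.73–1.17 × ULN and never reaches Grade 2.
- Over the same range the entry limit (159.1 µmol/L at 88.4) is 1.10–1.77 × ULN and never reaches Grade 3.
- If a leading digit was lost (assumption: 114.4 = 1.3 × 88, in the pattern of 105.6 = 1.2 × 88), Grade 3 would start above 343.2 and Grade 4 above 686.4 µmol/L.

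**The case against.** **Reach.** The fallback applies only when an institution's limit is unavailable. Protocol 10.4 requires each site file to hold normal ranges for the protocol's laboratory tests, and creatinine is among those tests in Protocol Appendix D. The fallback should therefore be needed seldom, perhaps never. This stands as a limit on size. It does not make the constant right: the SAP wrote the rule for exactly this case, and the documents do not say how often it will arise.

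**Source of the figure.** The text was read from a PDF, and a digit may have been lost in reading. That cannot be excluded, so the first action is to look at the source file.

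**Other TLS reporting.** SAP 7.11.2 also reports TLS through a standardized MedDRA query with CTCAE grades, which do not use this fallback. That is correct, and it limits the harm to the tables by maximum TLS grade.

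**Stronger readings a reader might infer.**
- That men with normal creatinine in general would be graded 3–4. They would not: laboratory TLS and a missing institutional limit must both be present.
- That the Grade 1 renal cell, which has no lower bound, turns every laboratory-TLS patient at every site into a clinical case. SAP 7.11.3 requires elevated creatinine, arrhythmia or seizure before Appendix 1 grading applies, and the table layout keeps a separate row for laboratory TLS without clinical manifestations. With a correct ULN the cell is loose wording, not a second error.
- That the error biases the comparison against ACM. The direction would depend on how men with laboratory TLS and no institutional limit divide between the arms, which the documents do not give.

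**Conclusion.** The point holds in a limited form. As printed, the male fallback ULN of 14.4 µmol/L is inconsistent with the female value beside it by a factor of 7.33. It places any male creatinine above 43.2 µmol/L in renal Grade 3 and above 86.4 µmol/L in Grade 4. A man at the protocol's entry limit would sit at about 11 × ULN.

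It affects only men with laboratory TLS whose institution's limit is missing. That number is unknown and is probably small. For them the maximum-grade TLS tables would show false Grade 3–4 clinical TLS. Nothing reaches the primary endpoint, alpha or sample size.

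The 7.33 ratio and the µmol/L thresholds rest on the SAP's own numbers. The mg/dL figures assume 88–88.4 µmol/L per mg/dL. That a digit was dropped is an inference.

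**What to change.** Check the SAP source file. If 14.4 is what is printed, replace the male fallback ULN with the value confirmed from the sponsor's own source before TLS grading is programmed. The documents do not supply the correct value, so 114.4 should be treated only as a candidate to verify.

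Optional wording: label the Grade 1 renal cell as above ULN to 1.5 × ULN, so that it matches the elevated-creatinine condition in 7.11.3.

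Cost: one number in a footnote and, if wanted, one table cell. No change to data collection or trial conduct.
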